1.0 PROTOCOL SUMMARY AND/OR SCHEMA

Cutaneous T-cell lymphoma: TNM stages IB, IIA, IIB-IV, either newly diagnosed or previously treated with active measurable disease

Sample Size: 37 patients

Multi-Center Study : Participating sites include M.D. Anderson Cancer Center, Yale University School of Medicine, New York University Medical Center, Hackensack University Medical Center

IND Status: Non-IND

Criteria to be used for response evaluation:

The evaluation of cutaneous tumor burden in CTCL is an evolving process. Skin tumor and lymph node assessments will be performed prior to treatment and after eight cycles of Doxil® according the Severity-Weighted Assessment Tool (SWAT) for CTCL response that is currently employed in IRB 02-078 and 04-051. Also the completion of treatment, history and general physical examination, Karnofsky performance status, CBC with Sézary cell count for patients with Sézary syndrome, and CT scans of the chest, abdomen and pelvis for patients with TNM stage IV CTCL will be obtained. These studies will also be obtained prior to treatment. If clinical complete remission of target skin lesions is suspected, skin biopsies will be repeated following completion of treatment.

Dosing/Regimen:

1. Doxil®Dose: 20mg/m² intravenously. Frequency: 2 weeks. Number of Cycles: 8
2. Targretin®Dose: 300mg/m² orally Frequency: Daily for at least 16 weeks

Schema:

Doxil® every 2 weeks x 8→response assessment→Targretin® x 16 weeks→response assessment, CR/PR→continue Targretin® until relapse.

2.0 OBJECTIVES AND SCIENTIFIC AIMS

Primary Objective: To determine the progression-free survival in patients with CTCL treated by Doxil® followed by Targretin®

Secondary Objective: To determine the major response rate (CR + PR) of Doxil® followed by Targretin® in the treatment of CTCL

**Memorial Sloan-Kettering Cancer Center
IRB Protocol**

IRB#: 05-098 A(6)

3.0 BACKGROUND AND RATIONALE

Cutaneous T-cell lymphoma (CTCL) is a chronic lymphoma that is not curable with systemic treatment. Doxorubicin is one of many single agents with activity in CTCL¹. Doxorubicin HCl liposome injection (Doxil®) is licensed for the treatment of Kaposi's sarcoma. High concentrations are attained in skin lesions of Kaposi's sarcoma following intravenous administration of Doxil®. At 48 and 96 hours post-infusion of Doxil® 20mg/m² in 11 patients, the concentrations of Doxil® in biopsies of skin lesions of Kaposi's sarcoma were several-fold higher than in those in normal skin. Adverse events led to discontinuation of Doxil® in only 5% of patients with Kaposi's sarcoma treated at this dose. Wollina et al.² treated 34 CTCL patients with Doxil; 27 received Doxil at a dose of 20 mg/m² every 2-4 weeks, 23 of whom were treated every 4 weeks. The major response rate was 88.2% with 15 patients achieving a CR or CRu (not confirmed by skin biopsy) and 15 a PR. Event-free survival was 12.0 months ± 9.5 months. Only 6 patients experienced grade 3 or 4 toxicities. Prince and colleagues³ reported on two patients with CTCL who failed to respond to Doxil®. Both were refractory to other previously administered intravenous chemotherapy. Although the Package Insert for Doxil® recommends a dose of 20 mg/m² administered every 3 weeks for Kaposi's sarcoma, the safety and efficacy of this dose administered every two weeks has been recently established for breast cancer^{4,5}.

Bexarotene (Targretin®) is a synthetic retinoid that selectively activates retinoid X receptors (RXRs). These retinoid receptors have biologic activity distinct from that of retinoic acid receptors (RARs). Once activated, these receptors function as transcription factors that regulate the expression of genes that control cellular differentiation and proliferation. By mechanisms that are not known, activity has been found against CTCL, and the drug has been recently commercially released. The optimal dose was 300 mg/m²/day, and patients on the trials were treated for up to 97 weeks. At the optimal dose, in patients with refractory or persistent early stage CTCL, the overall response rate was 54% and was 45% for patients with refractory advanced stage disease^{6,7}. At this dose, most side effects were infrequent and included pruritus, headache, peripheral edema, leukopenia, hypothyroidism and rash. Grade 3 or 4 hypertriglyceridemia and hypercholesterolemia were seen in 25%-30% of patients. These elevations are reversible with cessation of the drug, and some patients were continued on treatment with the addition of antilipemic treatment.

There are no preclinical data on potential synergy of Doxil® and Targretin®. Sequential treatment with single agents in patients with CTCL has been as effective as and less toxic than the use of drug combinations⁸.

Memorial Sloan-Kettering Cancer Center
IRB Protocol

IRB#: 05-098 A(6)

Further organized phase II investigation of Doxil® followed by Targretin® treatment of CTCL seems warranted in view of the following considerations:

1. Treatment of patients with CTCL with both agents results in high response rates.
2. The high skin lesion concentrations and efficacy were seen in the treatment of Kaposi's sarcoma with Doxil®.
3. Severe adverse events were infrequent in patients with Kaposi's sarcoma or CTCL treated at the doses proposed in this study.
4. Although Doxil® alone results in a high overall response rate, the responses of at least 50% of the patients are incomplete, and progression-free survival can be relatively short.
5. Although cardiotoxicity is less with Doxil® than doxorubicin, concern about eventual cardiac toxicity might limit the continuous use of Doxil® as a maintenance drug. The responses with Doxil® might be more rapid than with Targretin®. The latter agent might improve on initial responses to Doxil® and maintain complete and partial remissions for a longer time than a brief course of Doxil® alone.

4.0 OVERVIEW OF STUDY DESIGN/INTERVENTION

4.1 Design

This is a phase II, multi-center, open-label, single arm trial. The goals are to prolong progression-free survival and improve response rate in patients with cutaneous T-cell lymphomas with the sequential use of Targretin after an optimal course of Doxil

4.2 Intervention

Patients will be treated with intravenous Doxil® every two weeks for 8 doses (16 weeks). Responses will be assessed. They will then receive Targretin® orally for at least 16 weeks. Patients who achieve a CR or PR may continue on Targretin® until relapse.

5.0 THERAPEUTIC/DIAGNOSTIC AGENTS

Doxil® (doxorubicin HCl liposome injection)

Doxil® (doxorubicin HCl liposome injection) is doxorubicin hydrochloride (HCl) encapsulated in STEALTH® liposomes for intravenous administration. The active ingredient of Doxil® is doxorubicin HCl, a cytotoxic anthracycline antibiotic isolated from *Streptomyces peucetius* var. *caesius*. The mechanism of action of doxorubicin HCl is thought to be related to its ability to bind DNA and inhibit nucleic acid synthesis. Cell structure studies have demonstrated rapid cell penetration and perinuclear chromatin binding, rapid inhibition of mitotic activity and nucleic acid synthesis, and induction of mutagenesis and chromosomal aberrations.

If at anytime the patient develops progressive disease he/she will be taken off study and referred for alternative therapy.

**Memorial Sloan-Kettering Cancer Center
IRB Protocol**

IRB#: 05-098 A(6)

If at anytime the patient develops unacceptable toxicity he/she will be removed from study.

If at anytime the patient is found to be ineligible for the protocol as designated in the section on Criteria for Patient/Subject Eligibility (i.e., a change in diagnosis), the patient will be removed from the study.

Doxil[®] is doxorubicin HCl encapsulated in long-circulating STEALTH[®] liposomes. Liposomes are microscopic vesicles composed of a phospholipid bilayer that are capable of encapsulating active drugs. The STEALTH[®] liposomes of Doxil[®] are formulated with surface-bound methoxypolyethylene glycol (MPEG), a process often referred to as pegylation, to protect liposomes from detection by the mononuclear phagocyte system (MPS) and to increase blood circulation time.

Doxil[®] (doxorubicin HCl liposome injection) is indicated for:

DOXIL[®] (doxorubicin HCl liposome injection) is indicated for the treatment of patients with ovarian cancer whose disease has progressed or recurred after platinum-based chemotherapy.

DOXIL[®] (doxorubicin HCl liposome injection) is also indicated for the treatment of AIDS-related Kaposi's sarcoma in patients with disease that has progressed on prior combination chemotherapy or in patients who are intolerant to such therapy.

These indications are based on objective tumor response rates. No results are available from controlled trials that demonstrate a clinical benefit resulting from this treatment, such as improvement in disease-related symptoms or increased survival.

Doxil Study Drug Supplier/Accountability

Doxil will be provided by Ortho Biotech Products, L.P. The investigator agrees not to supply the study drug to any person other than investigators, designated staff and the subjects participating in the study. It is the responsibility of the clinical investigator to ensure that all study drug received at the site will be inventoried and accounted for throughout the study. Records must be kept by the institution. Administration of the study drug must be recorded in the patient's permanent record. The study drug provided may not be used for any purpose other than what is outlined in this protocol, including other human studies, animal investigations or in vitro testing. Study drug will be stored in a limited access or locked area and under refrigeration.

Doxil Storage and Handling

Refrigerate unopened vials of Doxil[®] at 2°C to 8°C (36°F to 46°F). Avoid freezing. Prolonged freezing may adversely affect liposomal drug products; however, short-term freezing (less than 1 month) does not appear to have a deleterious effect on Doxil[®].

Memorial Sloan-Kettering Cancer Center
IRB Protocol

IRB#: 05-098 A(6)

Caution should be exercised in the handling and preparation of Doxil[®]. The use of gloves is required. If Doxil[®] comes into contact with skin or mucosa, immediately wash thoroughly with soap and water.

[figure not shown]
Doxil[®] should be considered an irritant and precautions should be taken to avoid extravasation. With intravenous administration of Doxil[®], extravasation may occur with or without an accompanying stinging or burning sensation, even if blood returns well on aspiration of the infusion needle. If any signs or symptoms of extravasation have occurred, the infusion should be immediately terminated and restarted in another vein. Doxil[®] must not be given by the intramuscular or subcutaneous route.

Doxil[®] should be handled and disposed of in a manner consistent with other anticancer drugs. Several guidelines on this subject exist.

Targretin[®] (bexarotene)

Targretin[®] (bexarotene) is a member of a subclass of retinoids that selectively activate retinoid X receptors (RXRs). These retinoid receptors have biologic activity distinct from that of retinoic acid receptors (RARs). Each soft gelatin capsule for oral administration contains 75 mg of bexarotene.

The chemical name is 4-[1-(5,6,7,8-tetrahydro-3,5,5,8,8-pentamethyl-2-naphthalenyl) ethenyl] benzoic acid, and the structural formula is as follows:

Bexarotene is an off-white to white powder with a molecular weight of 348.48 and a molecular formula of C₂₄H₂₈O₂. It is insoluble in water and slightly soluble in vegetable oils and ethanol, USP.

Each Targretin[®] (bexarotene) capsule also contains the following inactive ingredients: polyethylene glycol 400, NF, polysorbate 20, NF, povidone, USP, and butylated hydroxyanisole, NF. The capsule shell contains gelatin, NF, sorbitol special-glycerin blend, and titanium dioxide, USP.

Bexarotene selectively binds and activates retinoid X receptor subtypes (RXRa, RXRb, RXRg). RXRs can form heterodimers with various receptor partners such as retinoic acid receptors (RARs), vitamin D receptor, thyroid receptor, and peroxisome proliferator activator receptors (PPARs). Once activated, these receptors function as transcription factors that regulate the expression of genes that control cellular differentiation and proliferation. Bexarotene inhibits the growth *in vitro* of some tumor cell lines of hematopoietic and squamous cell origin. It also induces tumor

**Memorial Sloan-Kettering Cancer Center
IRB Protocol**

IRB#: 05-098 A(6)

regression *in vivo* in some animal models. The exact mechanism of action of bexarotene in the treatment of cutaneous T-cell lymphoma (CTCL) is unknown.

Targretin® capsules were evaluated in 152 patients with advanced and early stage cutaneous T-cell lymphoma (CTCL) in two multicenter, open-label, historically controlled clinical studies conducted in the U.S., Canada, Europe, and Australia.

The advanced disease patients had disease refractory to at least one prior systemic therapy (median of two, range one to six prior systemic therapies) and had been treated with a median of five (range 1 to 11) prior systemic, irradiation, and/or topical therapies. Early disease patients were intolerant to, had disease that was refractory to, or had reached a response plateau of six months on, at least two prior therapies. The patients entered had been treated with a median of 3.5 (range 2 to 12) therapies (systemic, radiation, and/or topical).

The two clinical studies enrolled a total of 152 patients, 102 of whom had disease refractory to at least one prior systemic therapy, 90 with advanced disease and 12 with early disease. This is the patient population for whom Targretin® capsules are indicated. Patients were initially treated with a starting dose of 650 mg/m²/day with a subsequent reduction of starting dose to 500 mg/m²/day. Neither of these starting doses were tolerated, and the starting dose was then reduced to 300 mg/m²/day. If, however, a patient on 300 mg/m²/day of Targretin® capsules showed no response after eight or more weeks of therapy, the dose could be increased to 400 mg/m²/day. Tumor response was assessed in both studies by observation of up to five baseline defined index lesions using a Composite Assessment of Index Lesion Disease Severity (CA). This endpoint was based on a summation of the grades, for all indexes lesions, of erythema, scaling, plaque elevation, hypopigmentation or hyperpigmentation, and area of involvement. Also considered in response assessment was the presence or absence of cutaneous tumors and extracutaneous disease manifestations.

All tumor responses required confirmation over at least two assessments separated by at least four weeks. A partial response was defined as an improvement of at least 50% in the index lesions without worsening, or development of new cutaneous tumors or non-cutaneous manifestations. A complete clinical response required complete disappearance of all manifestations of disease, but did not require confirmation by biopsy.

At the initial dose of 300 mg/m²/day, 1/62 (1.6%) of patients had a complete clinical tumor response and 19/62 (30%) of patients had a partial tumor response. The rate of relapse (25% increase in CA or worsening of other aspects of disease) in the 20 patients who had a tumor response was 6/20 (30%) over a median duration of observation of 21 weeks, and the median duration of tumor response had not been reached. Responses were seen as early as 4 weeks and new responses continued to be seen at later visits.

**Memorial Sloan-Kettering Cancer Center
IRB Protocol**

IRB#: 05-098 A(6)

Targretin® capsules are supplied as 75-mg off-white, oblong soft gelatin capsules, imprinted with “Targretin,” in high density polyethylene bottles with child-resistant closures.

Bottles of 100 capsules..... NDC 64365-502-01

Store at 2°-25°C (36°-77°F). Avoid exposing to high temperatures and humidity after the bottle is opened. Protect from light.

Manufactured for: Ligand Pharmaceuticals Incorporated
San Diego, CA 92121
by: R.P. Scherer
St. Petersburg, FL 33716

6.0 CRITERIA FOR SUBJECT ELIGIBILITY

6.1 Subject Inclusion Criteria

- Patient \geq 18 years of age.
- Cutaneous T-cell lymphoma: TNM stages IB, IIA, IIB-IV with biopsy documentation within six weeks before treatment. Repeat biopsies are not required within six weeks before treatment for patients with Sézary syndrome and objective evidence of circulating cells.
- KPS \geq 60
- Acceptable organ function: absolute neutrophil count \geq 1500/ μ L, platelet count \geq 100,000/ μ L, bilirubin \leq 1.5x upper limit of normal, creatinine \leq 1.5x upper limit of normal, SGOT (AST) and SGPT (ALT) \leq 2.5x upper limit of normal
- MUGA or 2-d echocardiogram indicating an ejection fraction of \geq 50% within 42 days prior to first dose of study drug. The method used at baseline must be used for later monitoring.
- Patients previously treated with doxorubicin or epirubicin are eligible if the total cumulative dose does not exceed 300 mg/m² for doxorubicin or 540 mg/m² for epirubicin.
- Negative pregnancy test. Effective birth control measures.
- Topical corticosteroids, with the exception of those with high potency (class 1), will be allowed for patients with erythroderma-Sézary syndrome (T4) and tumor stage (T3) with intense pruritus. Therapy with non-prescription emollients will also be allowed on study.

**Memorial Sloan-Kettering Cancer Center
IRB Protocol**

IRB#: 05-098 A(6)

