6.2 Subject Exclusion Criteria

- Pregnant or lactating women
- No acute intercurrent disease including active potentially life-threatening infection or heart disease, with New York Heart Association Class II or greater, or clinical evidence of congestive heart failure.
- History of hypersensitivity reactions attributed to a conventional formulation of doxorubicin HCL or components of Doxil
- No demonstrated resistance to prior treatment with Targretin®.
- Patients using class 1 high potency topical therapy will not be allowed on to the study.

Please note copies of source documentation confirming eligibility for patients enrolling at outside institutions must be provided to the MSKCC CTO registrar at the time of registration. Please fax to [contact].

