The patient's palm with 4 fingers is traced on a transparency sheet at the baseline visit, using a permanent marker that will not rub off or smear. The transparency of the patient's palm should be used in all SWAT assessments during the course of the clinical study. The transparency will be labeled with the patient's study ID number kept in the patient's study file on site. Using the baseline visit transparency of the patient's palm, the investigator will measure and record on the case report form (Example of table from CRF is given below) the %TBSA for each lesion type within each of the 12 regions.

2. Severity Weighting Factor

The severity weighting factors will be the following:

**Memorial Sloan-Kettering Cancer Center
IRB Protocol**

IRB#: 05-098 A(6)

1= patch (flat erythema or erythema with mild infiltration)
2=plaque (e levated erythema or erythema with moderate infiltration)

4= tumor or ulceration (erythema with fissuring, ulceration or tumor)

Patch is defined as abnormal skin not elevated from normal skin. A plaque is defined as abnormal skin elevated from normal skin by < 5 mm. A plaque elevated ≥5 mm is a tumor.

3. Calculating Skin Scores

The sum of %TBSA by lesion is derived by summing the %TBSA from all regions affected by the lesion. The sum of %TBSA across lesion types (patches, plaques and tumors) within each region can not exceed the %TBSA for the region. For example, the %TBSA for the head region is 7%. The sum of %TBSA across lesion types from head can only range from 0-7%. The skin score subtotal by lesion type are derived by multiplying the sum of %TBSA for patches from all regions by 1, sum of %TBSA of plaques from all regions by 2, and the sum of %TBSA of tumors or ulcers from all regions by 4. The skin score total is derived from summing the skin score subtotals for patches, plaques and tumors or ulcers. The skin score total is dimensionless with a scale of 0 to 400.

Region	% TBSA for the region	% TBSA Patch (or flat erythema)	% TBSA Plaque (or elevated/indurated erythema)	% TBSA Tumor/ Ulceration (or erythema w/fissuring, ulceration)
Head	7			
Neck	2			
Anterior Trunk	13			
Posterior Trunk	13			
Buttocks	5			
Genitalia	1			
Upper Arms	8			
Forearms	6			
Hands	5			
Thighs	19			
Lower Leg	14			
Feet	7			
% BSA by category	100			
Severity Weighting Factor		X 1	X 2	X 4
Skin Score Subtotal				

**Memorial Sloan-Kettering Cancer Center
IRB Protocol**

IRB#: 05-098 A(6)

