Responses will be determined by the criteria described in the table below. Progression of disease while on treatment should be confirmed by a second assessment 1-4 weeks later so that patients who experience a temporary flare of disease due to skin infection or other intercurrent illnesses are not removed from the study prematurely.

Assessment	Description	Status
Completely clear	No evidence of disease; 100% improvement	CCR
Marked Improvement	Greater than or equal to 50% decrease in skin scores compared to baseline and improvement is maintained for 4 weeks	PR
Slight Improvement	Less than 50% decrease in skin scores compared to baseline	SD
Worse	$\geq 25\%$ increase in skin scores compared to baseline while the patient is actively taking the study drug or $\geq 50\%$ increase in the sum of the products of the greatest diameters of pathologically positive lymph nodes (should be documented by biopsy) compared to baseline while the patient is actively taking the study drug.	PD

Assessment of Overall Skin Disease

Pruritus Relief (Appendix 1)

The intensity of pruritus will be evaluated by the patient at baseline, at the week 16 (end of treatment with Doxil®) and week 32 (after 16 weeks of treatment with Targretin®) using a 1-10 point scale, where 0 is no pruritus and 10 is the worst imaginable pruritus. A 3-point decrease in pruritus intensity confirmed by a second assessment at least 4 weeks later without an increase in the use of anti-pruritic medications is considered clinically significant in those whose pruritus score is ≥ 3 on the 0-10 point scale at baseline.

4. As a secondary goal, index lesion severity will be evaluated by a modified Composite Assessment Scale (Appendix 2). These are measurements of skin disease that have been employed and validated in the phase II-III studies of Targretin® and in the current MSKCC trial of Targretin® of Intron-A® (IRB #01-128) in CTCL. Up to 4 index skin lesions will be chosen from representative patch, plaque and tumor lesions, and erythrodermic lesions. For erythrodermic patients, a 10x10 cm. area, easily identified by anatomic landmarks will be chosen and assessed by the same scale. These index lesions will be photographed and assessed at the same time as the SWAT assessment.

In the Phase II-III studies of Targretin capsules in CTCL, the Composite Assessment (CA) of Index Lesion Disease Severity was based on a core element of the summation of index lesion

**Memorial Sloan-Kettering Cancer Center
IRB Protocol**

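### A topical steroid started or stepped up after baseline could contribute to a recorded PR, because neither the steroid allowance nor the PR rule addresses changes in use

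*Combined protocol and SAP*

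**What the plan says.** Section 6.1 states: "Topical corticosteroids, with the exception of those with high potency (class 1), will be allowed for patients" with T4 disease and with T3 disease and intense pruritus (the pruritus condition may attach to T3 alone or to both). It sets no condition on prior use, stable use or later changes. The next sentence reads "Therapy with non-prescription emollients will also be allowed on study", which suggests that the steroid allowance also runs into treatment. Section 6.2 adds a condition at entry: "Patients using class 1 high potency topical therapy will not be allowed on to the study".

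In Section 12.7 the PR row requires "Greater than or equal to 50% decrease in skin scores compared to baseline and improvement is maintained for 4 weeks". The skin score is built by "multiplying the sum of %TBSA for patches from all regions by 1, sum of %TBSA of plaques from all regions by 2"; tumor or ulcerated area carries a weight of 4, and flat erythema counts as patch. In the same section, a 3-point fall in itch, confirmed at least 4 weeks later, counts only "without an increase in the use of anti-pruritic medications is considered clinically significant".

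Section 14.0 names the response rates as secondary endpoints and gives them no threshold. Section 9.0 itself prescribes a betamethasone gel for hands and feet after a first Grade 1 toxicity. Appendix 4 lists a Concomitant Drug Form at baseline, by cycle and off study. No section links it to response grading.

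**The concern.** The skin score measures erythema and elevation by area. A topical steroid put on CTCL lesions after baseline could plausibly lower it. With no control arm, nothing in the design separates that contribution from the effect of the study drugs. At stake is the CR+PR rate, the stated secondary objective in Section 2.0. A patient just short of PR on study drug could be recorded as PR once a steroid is added, and continued use could hold the fall through the 4-week maintenance period.

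Steady use that began before baseline is not at issue, because it is already in the baseline score.

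**Working it through.** **1. The plan's own figure.** Inputs from Section 14.0: N = 37, success at 24 or more progression free, null rate 0.50 (median 12 months), target rate 0.70. Exact binomial: P(X ≥ 24 | 37, 0.50) = 0.0494 and P(X ≥ 24 | 37, 0.70) = 0.807. The design reproduces one-sided and is not in dispute here.

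**2. What each patient moves.** On 37 patients, k reclassified PRs move CR+PR by k/37. For assumed k of 1, 2 or 4 this is 2.7, 5.4 or 10.8 points. The documents give no basis for choosing k.

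**3. How much steroid effect turns SD into PR.** The weights (1, 2, 4) come from Section 12.7. Assume that study drug clears a fraction d of the disease and that the steroid acts on what remains.

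(a) *All plaque, area A, baseline score 2A.* If a fraction f of the remainder flattens to patch, the score is A(1−d)(2−f). PR needs this ≤ A, so f ≥ 2 − 1/(1−d).

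(b) *T3 example: 10% TBSA tumor plus 20% plaque, tumors assumed unaffected by the steroid.* Baseline is 10×4 + 20×2 = 80, so PR needs 40.
- d = 0.4: 6×4 + 12×2 = 48, and 8 points must be saved. Flattening saves 1 point per 1% TBSA, so 8/12 = 67% must flatten. Clearing saves 2, so 4/12 = 33% must clear.
- d = 0.3: 7×4 + 14×2 = 56, and 16 points must be saved. Flattening would need 16/14 = 114%, which is impossible. Clearing needs 8/14 = 57%.

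(c) *T4 flat erythema, weight 1.* Flattening saves nothing. If a fraction c clears, (1−d)(1−c) ≤ 0.5 gives c ≥ 1 − 1/(2(1−d)).

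| Share of the remainder needed | d = 0.4 | d = 0.3 | d = 0 |
|---|---|---|---|
| (a) plaque, flattening | 33% | 57% | 100% |
| (b) T3, plaque flattening | 67% | not reachable | – |
| (b) T3, plaque clearing | 33% | 57% | – |
| (c) T4 flat, clearing | 17% | 29% | 50% |

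The required effect rises quickly as d falls, so the exposure sits mainly with near-responders.

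**4. Existing safeguards.**
- The 4-week maintenance rule does not help if the steroid continues.
- Not viewing earlier SWAT scores limits biased scoring, not a real steroid effect.
- Biopsy applies only when clinical complete remission is suspected.
- Question 2 of Appendix 1 compares medication use only with the previous week, so an increase made weeks earlier can read as no change.

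**The case against.** The strongest reply is that the causal step lies outside the documents. Nothing in them says that a non-class-1 topical steroid lowers a SWAT score, and every magnitude above rests on assumed values. That stands, and it is why no estimate of bias is offered.

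The allowance also sits under inclusion criteria and may mean only that existing users can enroll. A reader might infer that the protocol invites new steroid use and that the PR rate is therefore inflated. The documents do not support that. They leave a start or step-up unaddressed, and they do not show that it happens.

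Foreseeability is modest. Section 3.0 says of Targretin that "most side effects were infrequent and included pruritus, headache, peripheral edema, leukopenia, hypothyroidism and rash", and the toxicity list in Section 11.2 includes rash but not pruritus. A steroid that clears a new drug rash removes erythema that was absent at baseline, so it does not by itself create a fall from baseline.

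The pruritus rule guards against drugs aimed at the symptom being scored, so it is a precedent for a medication condition rather than proof of an inconsistency.

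A reader might also infer that steroid use goes unrecorded during Targretin. That is doubtful. Appendix 4 lists the Toxicity and Physical Exam Forms under cycle and off study, while Appendix 3 requires both assessments at Targretin visits. Cycle collection of the Concomitant Drug Form therefore probably covers that phase too.

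What remains is that no rule says how a recorded steroid change affects PR.

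**Conclusion.** The point holds as a cheap improvement. A post-baseline start or step-up on CTCL lesions could contribute to a recorded PR, and the plan has no pre-specified way to show how far CR+PR depends on such patients. The size is 2.7 points per affected patient. How many are affected, and how strongly the steroid acts, cannot be found in the documents. The exposed group is the T3/T4 subset, of unstated size.

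It would be tempting to extend this to the primary endpoint. That would require a steroid to hold a patient whose only progression is in the skin below the 25% increase that defines PD. This is conditional and cannot be quantified, and the 24-of-37 rule is not contested. No decision threshold depends on CR+PR.

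**What to change.** In Sections 12.7 and 14.0, pre-specify a sensitivity CR+PR rate.

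- **Who is flagged.** Count as non-responders only those PR patients who started a topical corticosteroid on CTCL lesions, or raised its potency class or frequency, after baseline and either before the first score meeting the 50% fall or during its 4-week confirmation. A PR confirmed before the change is not flagged.
- **Drug rash.** Short courses that end before scoring are exempt.
- **Hand-foot gel (Section 9.0).** For users, rescore the sensitivity PR with the hands and feet regions (5% + 7% = 12% of TBSA) left out at both baseline and follow-up. The region-level SWAT entries already allow this.
- **Recording.** Enter steroid name, potency, frequency, site and dates on the Concomitant Drug Form, and confirm that it is completed at Targretin visits.

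CR+PR as written stays the main rate. CCR and its biopsy, the primary rule and permitted care do not change.

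The cost is a few sentences, one extra response rate and up to five fields on an existing form. If the form is not already completed at the Targretin visits at weeks 2, 4, 8, 12 and 16, the addition is at most 5 × 37 = 185 collections at visits already scheduled. The downside is that the sensitivity rate may understate some true T3/T4 responses.
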